11.3.2 Possible Treatment Emergent Adverse Events (TEAEs) for DS-3201b

COMMON:

- Platelet Count Decreased
- Altered taste (Dysgeusia)
- Anemia
- Neutrophil Count Decreased
- Alopecia
- White Blood Cell Count Decreased
- Lymphocyte Count Decreased
- Diarrhea
- Nausea

OCCASIONAL (Uncommon):

- Alanine Aminotransferase Increased
- Aspartate Aminotransferase Increased
- Decreased Appetite
- Common cold (Nasopharyngitis)
- Cough
- Fatigue
- Arthralgia
- Dyspnea
- Fever (Pyrexia)
- Pruritus
- Rash
- Dry Skin
- Gamma-Glutamyltransferase Increased

RARE:

- None

Contraindications regarding the use of DS-3201b in human subjects have not been established. DS-3201b is contraindicated for subjects with known hypersensitivity to either the drug substance or inactive ingredients in the drug product. No overdosages have been reported to date.

ADVERSE EVENTS OF SPECIAL INTEREST (AESI):

AESI include hepatic events that meet the potential Hy's Law criteria (defined as an elevated ALT and/or AST $\geq 3 \times$ ULN and an elevated TBL $> 2 \times$ ULN, regardless if it is due to disease progression per investigator assessment, which may occur at different time points during the study conduct), and secondary malignancy, including lymphoid malignancy.

Combined Elevations of Aminotransferases and Bilirubin

Hepatic events (both serious and non-serious) that meet the potential Hy's Law criteria defined as an elevated (ALT and/or AST) $\geq 3 \times$ ULN and an elevated TBL $> 2 \times$ ULN, regardless if it is due to disease progression per investigator assessment, that may occur at different time points during the study conduct, should always be reported to the sponsor. These events must be reported by eCRF, with the investigator's assessment of seriousness, severity, causality, and a detailed narrative. These events should be reported within 24 hours of investigator's awareness of the event regardless of seriousness.

If the subject discontinues study drug due to liver enzyme abnormalities, the subject should have additional clinical and laboratory evaluations in order to determine the nature and severity of the potential liver injury (including follow-up ALT, AST, TBL (including fractional), ALP and relevant hepatitis serology).

Secondary Malignancy

A 3-month nonclinical toxicology study in rats administered DS-3201b showed the potential risks of developing lymphoid malignancies. A follow-up 3-month study in older rats performed to further understand the pathogenic mechanisms of this above finding in younger rats showed administration of DS-3201b to aged rats did not induce a lymphoma that had been previously observed with younger rats. In addition, no similar findings were noted in other 3-month animal toxicity studies of DS-3201b. In the ongoing clinical development program cases of secondary malignancies have been reported (see IB version 7 for additional details).

The treatment of subjects with an EZH2 inhibitor may increase the risk of developing a secondary T-cell malignancy. T-cell lymphomas have been observed in animals treated with DS-3201b and other agents that inhibit EZH2 in repeat-dose toxicology studies. A pediatric patient treated with an EZH2 inhibitor (tazemetostat) developed a secondary T-cell lymphoblastic lymphoma after approximately 15 months of therapy. A dose or duration of therapy at which agents that inhibit EZH2 would not increase the risk of a secondary T-cell malignancy is currently unknown.

Subjects receiving DS-3201b should further be monitored for signs and symptoms of toxicities suggestive of secondary malignancy. Any confirmed new diagnosis of secondary malignancy

should be reported as adverse events of special interest and reported to the sponsor in an expedited manner. Generally, these events should be reported as SAEs (with at least a seriousness criterion of important medical event, unless other criteria are met).

11.4.3 Possible Treatment Emergent Adverse Events (TEAEs) for Irinotecan Irinotecan

COMMON:

- Fever
- Alopecia
- Neutropenia
- Leukopenia
- Thrombocytopenia
- Anemia
- Diarrhea
- Abdominal pain
- Asthenia (weakness)
- Anorexia
- Nausea
- Vomiting
- Constipation
- Mucositis
- Pain
- Infection

OCCASIONAL

- Cholinergic like-syndrome (acute)
- Chills
- Dizziness
- Weight loss
- Stomatitis
- Cough
- Dyspnea
- Diaphoresis
- Kidney dysfunction

RARE AND SERIOUS

- Dehydration secondary to diarrhea
- Neutropenic fever
- Anaphylaxis; anaphylactoid reaction

- Renal Failure
- Pulmonary toxicity: Interstitial lung disease or events; discontinue therapy upon diagnosis

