	
dose level for subsequent cycles. Further dose reductions must be discussed with the study PI and sponsor. If patient is already at the lowest dose of study drug, please discuss with the study PI and Daiichi regarding study continuation or discontinuation decision.
 
• Transfusion of red blood cells as per treating physician discretion is allowed.• For any dose delays greater than 28 days, decision regarding study continuation or discontinuation should be discussed with the study PI and Daiichi.
--	--

*Please see Section 11.7 for more details on the use of G-CSF in the setting of severe neutropenia or neutropenic fever.

Dose Modifications with Concomitant Strong CYP3A Inhibitors and/or P-gp Inhibitors

When drugs with strong CYP3A inhibitory effect and/or P-gp inhibitory effect are coadministered, the dose of the study drug should be reduced according to table 5.1. The dose of the study drug should be returned to the previous dose level that the subject was given after 3 days from the last dose of the concomitant strong CYP3A inhibitors and/or P-gp inhibitors.

Table 5.1 Dose Delays and Modifications for Concomitant Strong CYP3A Inhibitors and/or P-gp Inhibitors

Inhibitor	DS-3201b Dose	
	200 mg Once Daily	150 or 100 mg Once Daily*
Strong CYP3A inhibitors	Reduce the dose of the study drug to 100 mg once daily	Reduce the dose off the study drug to 50mg once daily
P-gp inhibitors	Reduce the dose of the study drug to 100 mg once daily	Reduce the dose off the study drug to 50mg once daily
Drugs having a strong CYP3A inhibitory effect and a P-gp inhibitory effect	Reduce the dose off the study drug to 50mg once daily	Interrupt the study drug

CYP3A = cytochrome P4503A; P-gp = P-glycoprotein

*When the dose of study drug DS-3201b is 150mg or 100mg once daily, the investigator should consult Daiichi's medical monitor before further reduction of the dose due to concomitant use of strong CYP3A or/and P-gp inhibitors.

Table 6.0 Dose Delays and Modifications for All Other Non-Hematologic TEAEs

Toxicity Grade	Modification instructions

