Other Non-Laboratory Adverse	
 Interrupt administration of study drug DS-3201b up to 28 days.

Events (drug related Grade 3 that require treatment)	
Resume the study drug DS-3201b at the dose before interruption once resolved to \leqGrade 1 or baseline value within 28 days after interrupting study drug.If a second dose interruption is required for the same drug-related adverse event, then decrease study drug DS-3201b dose by 1 dose level for subsequent cycles. Further dose reductions must be discussed with the study PI and sponsor. If patient is already at the lowest dose of study drug, please discuss with the study PI and Daiichi regarding study continuation or discontinuation decision. Exceptions:
○ Fatigue (DS-3201b related), Grade 3, that improves within 72 hours after onset○ Nausea, vomiting, anorexia, or diarrhea (DS-3201b related), Grade 3, that improves to \leqGrade 2 within 72 hours after onset with appropriate supportive therapy
Other Non-Laboratory Adverse Events (Grade 4, regardless of causality)	
Interrupt administration of study drug DS-3201b up to 28 days.If causality is attributed to study drug DS-3201b, resume the study drug DS-3201b at a reduced dose (by 1 dose level) for the subsequent cycles once resolved to \leqGrade 1 or baseline condition.If causality is not attributed to the study drug DS-3201b, resume the study drug DS-3201b at the dose before interruption or at a reduced dose (by 1 dose level).If second dose interruption is required due to the same drug-related adverse event, discontinue subject from the study.For any dose delays greater than 28 days, decision regarding study continuation or discontinuation should be discussed with the study PI and sponsor.

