Other Laboratory Adverse Events (DS-3201b drug related Grade 3 that require treatment)	
Interrupt administration of study drug DS-3201b up to 28 days.Resume the study drug DS-3201b at the dose before interruption once resolved to \leqGrade 1 or baseline value within 28 days after interrupting study drug.If a second dose interruption is required for the same drug-related adverse event, then decrease study drug DS-3201b dose by 1 dose level for subsequent cycles. Further dose reductions must be discussed with the study PI and sponsor. If patient is already at the lowest dose of study drug, please discuss with the study PI and Daiichi regarding study continuation or discontinuation decision. Exceptions:
○ Transient laboratory abnormalities (DS-3201b-related) that do not involve associated clinical signs or symptoms and that resolve within 72 hours after onset

	
For any dose delays greater than 28 days, decision regarding study continuation or discontinuation should be discussed with the study PI and sponsor.
Other Laboratory Adverse Events (DS-3201b drug related Grade 4)	
Interrupt administration of study drug DS-3201b up to 28 days.Resume the study drug DS-3201b at a reduced dose (by 1 dose level) for the subsequent cycles once resolved to \leqGrade 1 or baseline conditionIf a second dose interruption is required for the same drug-related adverse event, discontinue subject from studySubjects who experience a \geqGrade 3 laboratory AE who are, in the opinion of the investigator, benefiting from treatment may be allowed to continue study drug.
Other Non-Laboratory and Laboratory Adverse Events (regardless of causality, any AE, lab abnormality or intercurrent illness that presents a substantial clinical risk to the subject with continued dosing per the investigator's opinion)	
Interrupt administration of study drug DS-3201b until there is no longer a substantial clinical risk to the subject with continued dosing of the study drug DS-3201b per the investigator's opinionResume the study drug DS-3201b at the same dose level
AEs Grade 1-2	
Proceed with full-dose treatment of all agents.

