When administered in combination with other agents, or as a single agent, a reduction in the starting dose by at least one level of irinotecan should be considered for patients known to be homozygous for the UGT1A1*28 allele.

If dose level reduction below Level -2 is needed to manage toxicity due to irinotecan, then study treatment with both DS-3201b and irinotecan will be permanently discontinued.

Table 7.0 Dose Levels for Irinotecan^a

Starting Dose	125 mg/m ²
Dose Level -1	100 mg/m ²
Dose Level -2	75 mg/m ²

^a As per standardized prescribing information in the United States.

Table 8.0 Recommended Dose Modifications for Irinotecan in Combination-Regimens

CTCAE v5.0 Toxicity Grade	During a Cycle of Therapy	At the Start of Subsequent Cycles of Therapy ^a
No toxicity	Maintain dose level	Maintain dose level

Neutropenia*		
1 (1500 to 1999/mm ³)	Maintain dose level	Maintain dose level
2 (1000 to 1499/mm ³)	↓ 1 dose level	Maintain dose level
3 (500 to 999/mm ³)	Omit dose until resolved to ≤ grade 2, then ↓ 1 dose level	↓ 1 dose level
4 (<500/mm ³)	Omit dose until resolved to ≤ grade 2, then ↓ 2 dose levels	↓ 2 dose levels
Neutropenic fever	Omit dose until resolved, then ↓ 2 dose levels	
Other hematologic toxicities	Dose modifications for leukopenia or thrombocytopenia during a cycle of therapy and at the start of subsequent cycles of therapy are also based on NCI toxicity criteria and are the same as recommended for neutropenia above.	
Diarrhea^c		
1 (≤4 stools/day > pretx ^b)	Delay dose until resolved to baseline, then give same dose	Maintain dose level
2 (4-6 stools/day > pretx)	Omit dose until resolved to baseline, then ↓ 1 dose level	Maintain dose level
3 (≥7 stools/day > pretx; hospitalization indicated)	Omit dose until resolved to baseline, then ↓ 1 dose level	↓ 1 dose level
4 (life-threatening; urgent intervention indicated)	Omit dose until resolved to baseline, then ↓ 2 dose levels	↓ 2 dose levels
Other non-hematologic toxicities^d		
1	Maintain dose level	Maintain dose level
2	Omit dose until resolved to ≤ grade 1, then ↓ 1 dose level	Maintain dose level
3	Omit dose until resolved to ≤ grade 2, then ↓ 1 dose level	↓ 1 dose level
4	Omit dose until resolved to ≤ grade 2, then ↓ 2 dose levels	↓ 2 dose levels

*Please see Section 11.7 for more details on the use of G-CSF in the setting of severe neutropenia or neutropenic fever.

^a Relative to the starting dose in the previous cycle.

^b Pretreatment.

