^c Loperamide as needed can be administered to the patient for relief of symptoms once the toxicity grade has been determined. The dosing and frequency of loperamide can vary per patient and will be determined by the treating physician.

^d Excludes alopecia, anorexia, asthenia.

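### The irinotecan toxicity list ends therapy on a diagnosis of interstitial lung disease, but the general rows of Tables 8.0 and 6.0 would allow continuation or restart, and nothing reconciles them

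*Combined protocol and SAP*

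**What the plan says.** Section 11.4.3 lists possible adverse events of irinotecan. The last entry under the rare and serious events contains an instruction: "Pulmonary toxicity: Interstitial lung disease or events; discontinue therapy upon diagnosis".

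The dose rules are in two other places.

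- **Section 11.6, Table 8.0 (irinotecan).** A block for other non-hematologic toxicities gives an action for each grade. For Grade 2 during a cycle it is "Omit dose until resolved to ≤ grade 1, then ↓ 1 dose level". The footnote to the block reads "Excludes alopecia, anorexia, asthenia".
- **Section 11.5.4, Table 6.0 (DS-3201b).** The title is "Table 6.0 Dose Delays and Modifications for All Other Non-Hematologic TEAEs". For Grade 1-2 events the action is "Proceed with full-dose treatment of all agents". For a drug-related non-laboratory Grade 3 event that needs treatment, DS-3201b is interrupted, and the restart text begins "Resume the study drug DS-3201b at the dose before interruption once resolved to". Grade 4 has its own row, which ends "If second dose interruption is required due to the same drug-related adverse event, discontinue subject from the study".

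Neither table names ILD, pneumonitis or pulmonary toxicity, and neither refers to Section 11.4.3. Section 13.1 ends treatment for unacceptable adverse events, and for changes in the patient's condition that the investigator judges to rule out further treatment. It does not mention ILD.

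**The concern.** A stopping instruction sits inside a list of side effects, while the tables that sites use to decide on dosing do not carry it. An investigator who works from Section 11.4.3 would discontinue on diagnosis. One who works from the tables could continue a Grade 1 case without a hold, or restart a higher-grade case after recovery. Both could say that they followed the protocol.

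The scope of *therapy* is also open. Section 11.6 makes irinotecan adjustments independent of DS-3201b and lets DS-3201b continue while irinotecan is held, provided that the event is not also attributed to DS-3201b. It therefore matters whether the instruction covers one drug or two. Elsewhere, where both drugs must stop (a reduction below the lowest dose level, in Sections 11.5.4 and 11.6), the protocol names both.

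At stake are the safety of a patient with a serious lung event, and the same handling of that event at the two centres that take part in Phase II (Section 4.1).

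**Working it through.** No arithmetic applies, because the point depends on no sample size, error rate or event rate. The check sets the instructions side by side for one non-laboratory, non-hematologic event, ILD.

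| Grade | Section 11.4.3 | Table 8.0, irinotecan (during a cycle) | Table 6.0 |
|---|---|---|---|
| 1 | Discontinue | Maintain | Full dose, all agents |
| 2 | Discontinue | Omit until Grade 1 or lower, then down one level | Full dose, all agents |
| 3 | Discontinue | Omit until Grade 2 or lower, then down one level | If drug-related and needing treatment: interrupt DS-3201b, resume at the prior dose after recovery |
| 4 | Discontinue | Omit until Grade 2 or lower, then down two levels | Interrupt DS-3201b; after recovery resume one level lower if attributed to it, otherwise at the prior or a reduced dose; discontinue at a second interruption for the same drug-related event |

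1. **Do the general rows reach ILD?** By their wording, yes. Table 6.0 covers all other non-hematologic events. The block in Table 8.0 leaves out only alopecia, anorexia and asthenia.
2. **Irinotecan.** Section 11.4.3 and Table 8.0 differ at all four grades. At Grade 1 Table 8.0 has no hold. At Grades 2 to 4 it holds the drug first and allows a restart only after recovery. For the start of subsequent cycles, its Grade 2 entry is to maintain the dose level.
3. **The Grade 1-2 row of Table 6.0.** This row speaks of all agents, so it conflicts with Section 11.4.3 whichever drug *therapy* means.
4. **Grades 3 and 4 of Table 6.0.** These rows govern DS-3201b. They conflict with Section 11.4.3 only if *therapy* includes DS-3201b. When DS-3201b is held, Section 11.5.4 says that irinotecan should be held as well.
5. **Does another row supply the stop?** No. The Table 6.0 row for events that the investigator regards as a substantial clinical risk interrupts DS-3201b and then resumes it at the same level.
6. **Does Section 13.1 supply it?** It gives authority to stop. It does not make an ILD diagnosis a mandatory stop, and it does not say which drugs are affected.

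**The case against.** The strongest reply is that the protocol contains only one ILD instruction. The table rows are general, and a specific instruction is ordinarily read ahead of a general one. Table 8.0 is headed as recommended modifications, and Section 11.6 refers to usual clinical practice. Section 13.1 lets any investigator stop. The instruction is in the irinotecan list, and the DS-3201b list in Section 11.3.2 does not mention ILD, so most of Table 6.0 may be the wrong comparison.

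Much of this stands. A reader might infer that the protocol gives two explicit and opposite ILD rules. The documents do not support that: this is a specific instruction left unreconciled with general rows. A reader might also infer that the tables keep a patient with ILD on drug at every grade. They do not: irinotecan is held at Grades 2 to 4 during a cycle, and DS-3201b is held at drug-related Grade 3 needing treatment and at Grade 4.

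The reply does not dispose of the point. The protocol states no order of precedence, and Sections 11.5.4 and 11.6 say that the outlined modifications will be used in all Phase II cycles. Other event-specific stops are written into the tables: a second Grade 3 QTc interruption, serious arrhythmia attributed to DS-3201b, and a second occurrence of thrombocytopenia with bleeding. A site would look for an ILD stop in the same place.

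Two wider inferences are also unsupported:

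- **Response rate.** Section 14.0 counts a response at any reassessment within 6 months and keeps all patients in the analysis. A response recorded before ILD counts under either instruction, and the documents show no effect beyond that.
- **Toxicity counts.** At Grade 3 or above, an event at least possibly related to treatment is a DLT under Section 11.9 whatever is done with the dose. At Grade 2, failing to complete 75% of dosing in the run-in plus Cycle 1 can make it a DLT. But Table 8.0 itself omits irinotecan at Grade 2, and one of the two planned doses is 1/2 = 50%. Whether the two instructions then classify a patient differently depends on timing, speed of recovery and which drug stops.

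**Conclusion.** The inconsistency is real and should be corrected. Section 11.4.3 calls for discontinuation on diagnosis at any grade, while the general rows, read literally, allow continuation or restart at each of Grades 1 to 4. The conflict is plainest at Grade 1, where both tables continue without a hold, and at Grade 2, where Table 6.0 gives full dose of all agents and Table 8.0 omits and then reduces irinotecan. That Grade 2 mismatch between the tables affects other non-hematologic toxicities too and is not evidence about ILD in particular.

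The conclusion rests on two readings: that the general rows apply to any event not excepted, and, for the Grade 3-4 rows of Table 6.0 only, that *therapy* includes DS-3201b. The number of patients affected cannot be stated. The documents give no ILD rate beyond placing it among rare and serious events. The case is one of patient safety and uniform conduct, not of bias in the efficacy result. It takes no view on which clinical instruction is right.

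**What to change.** Reconcile Section 11.4.3 with Table 8.0, Table 6.0 and Section 13.1 so that the protocol has one instruction for ILD. State whether it covers irinotecan, DS-3201b or both, and cross-reference it from both tables. Leave the general rows in place, because other toxicities need them. Adding ILD to the Table 8.0 exclusions would not be a neutral repair: it presupposes one answer, and beside alopecia, anorexia and asthenia it could be misread as needing no change of dose. Which instruction applies is for the sponsor's clinicians.

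The cost is a few words in a protocol amendment, with no added procedures or patients.

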11.5.4 Dose Delays and Modifications for DS-3201b

During Cycle 1 of Phase I dose-escalation, which includes the initial 7 days of safety run-in from Day -7 to Day 0, dose delays and modifications for DS-3201b will not be used unless a DLT has been declared for purposes of determining the MTD. The outlined dose delays and modifications for both DS-3201b and irinotecan will be used in all patients in Phase I Cycle 1 if DLT has been declared, in all subsequent cycles of Phase I, and in all cycles of Phase II of this study. If toxicities are encountered, dosing adjustments and delays of DS-3201b and/or irinotecan will be made based on determination of the likely causative agent as outlined above in Sections 11.2 and 11.3. Determination of the likely causative agent will be dependent on the treating physician if they feel that the toxicity is at least possibly related to either or both of the study drugs.

Please refer to Table 2 in Section 9.0 for full details regarding the dose levels for DS-3201b. An abbreviated version of Table 2.0 is shown below for reference.

Dose Level	DS-3201b Dose
Level -1	50 mg once daily
Level 1(Starting Dose)	100 mg once daily
Level 2	150 mg once daily
Level 3	200 mg once daily
Level 4	250 mg once daily
Level 5	300 mg once daily

If dose level reduction below Level -1 is needed to manage toxicity due to DS-3201b, then study treatment with both DS-3201b and irinotecan will be permanently discontinued unless discussed with the study PI.

Table 5.0 Dose Delays and Modifications for Hematologic TEAEs

ADVERSE EVENT GRADE	DOSE MODIFICATION INSTRUCTIONS
≥Grade 4 neutropenia (<0.5 x 10 ⁹ /L per NCI CTCAE v5.0) lasting >7 days	
• Interrupt administration of study drug DS-3201b up to 28 days.• Resume the study drug DS-3201b at the dose before interruption if lasting ≤7 days at a reduced dose (by 1 dose level). If lasting >7 days once resolved to ≤Grade 2
OR	


Febrile neutropenia \geq Grade 3
 
OR
 
neutropenia requiring supportive G-CSF therapy*
	
(neutrophil count $\geq 1.0 \times 10^9/L$) after discussion with PI and Daiichi.
 
• If a second dose interruption is required for the same event, then the study drug DS-3201b may be reduced 1 additional dose level for subsequent cycles. Further dose reductions must be discussed with the study PI and Daiichi. If patient is already at the lowest dose of study drug DS-3201b, please discuss with the study PI and Daiichi regarding study continuation or discontinuation decision.• If ANC does not recover to $\geq 1.0 \times 10^9/L$ within 28 days after interrupting study drug DS-3201b and reducing the dose, please discuss with the study PI and sponsor regarding study continuation or discontinuation decision.• Use of G-CSF is allowed for recurrent neutropenia as per treating physician discretion (except in DLT evaluation period in Phase I Dose Escalation). For patients at high-risk of neutropenia as per treatment physician's discretion, G-CSF can be used in the DLT evaluation period in Phase II.• For any dose delays greater than 28 days, decision regarding study continuation or discontinuation should be discussed with the study PI and sponsor.

Grade 4 Thrombocytopenia ($<25 \times 10^9/L$)
 
OR
 
\geqGrade 3 Thrombocytopenia ($<50 \times 10^9/L$) associated with \geqGrade 2 bleeding/ requiring transfusion
 
OR
 
Grade 3 thrombocytopenia ($<50 \times 10^9/L$) lasting >7 days
	
• For Grade 4 Thrombocytopenia: Interrupt administration of study drug DS-3201b up to 28 days.• For Grade 4 Thrombocytopenia: Resume the study drug DS-3201b at a reduced dose (by 1 dose level) if thrombocytopenia recovers to \leqGrade 2 (platelet count $\geq 50 \times 10^9/L$)• For Grade 4 Thrombocytopenia: If a second dose interruption is required due to Grade 4 thrombocytopenia, then the study drug DS-3201b may be reduced 1 additional dose level for subsequent cycles. Further dose reductions must be discussed with the study PI and Daiichi. If patient is already at the lowest dose of study drug DS-3201b, please discuss with the study PI and Daiichi regarding study continuation or discontinuation decision.• For \geqGrade 3 Thrombocytopenia ($<50 \times 10^9/L$) associated with \geqGrade 2 bleeding: First occurrence -

	
Interrupt administration of study drug DS-3201b up to 28 days. Resume the study drug at a reduced dose (by 1 dose level) once resolved to \leqGrade 2 (platelet count $\geq 50 \times 10^9/L$) or return to baseline levels within 28 days after interrupting study drug, whether transfusion is given or not. The study drug DS-3201b may be resumed at the same dose after discussion with the study PI and Daiichi.
 
• For \geqGrade 3 Thrombocytopenia ($< 50 \times 10^9/L$) associated with \geqGrade 2 bleeding: Second occurrence – Discontinue subject from the study• For \geqGrade 3 Thrombocytopenia ($< 50 \times 10^9/L$) lasting > 7 days: First occurrence - Interrupt administration of study drug DS-3201b up to 28 days. Resume the study drug DS-3201b at a reduced dose (by 1 dose level) once resolved to \leqGrade 2 (platelet count $\geq 50 \times 10^9/L$) or return to baseline levels within 28 days after interrupting study drug• For \geqGrade 3 Thrombocytopenia ($< 50 \times 10^9/L$) lasting > 7 days: Second occurrence – Interrupt administration of study drug DS-3201b up to 28 days. Resume the study drug at a reduced dose (by 1 dose level) once resolved to \leqGrade 2 (platelet count $\geq 50 \times 10^9/L$) or return to baseline levels within 28 days after interrupting study drug• For \geqGrade 3 Thrombocytopenia ($< 50 \times 10^9/L$) lasting > 7 days: Third occurrence - Discontinue subject from the study• For any dose delays greater than 28 days, decision regarding study continuation or discontinuation should be discussed with the study PI and sponsor.
\geq Grade 3 anemia (< 8.0 g/dL) requiring transfusion	
• Interrupt administration of study drug DS-3201b up to 28 days.• Resume the study drug DS-3201b at the dose before interruption once resolved to \leqGrade 2 (hemoglobin levels recovered to ≥ 8.0 g/dL) at least 7 days since transfusion, or baseline value within 28 days after interrupting study drug, or reduce 1 dose level with after discussion with study PI and Daiichi.• If a second dose interruption is required for the same event, then decrease study drug DS-3201b dose by 1

	
dose level for subsequent cycles. Further dose reductions must be discussed with the study PI and sponsor. If patient is already at the lowest dose of study drug, please discuss with the study PI and Daiichi regarding study continuation or discontinuation decision.
 
• Transfusion of red blood cells as per treating physician discretion is allowed.• For any dose delays greater than 28 days, decision regarding study continuation or discontinuation should be discussed with the study PI and Daiichi.
--	--

*Please see Section 11.7 for more details on the use of G-CSF in the setting of severe neutropenia or neutropenic fever.

Dose Modifications with Concomitant Strong CYP3A Inhibitors and/or P-gp Inhibitors

When drugs with strong CYP3A inhibitory effect and/or P-gp inhibitory effect are coadministered, the dose of the study drug should be reduced according to table 5.1. The dose of the study drug should be returned to the previous dose level that the subject was given after 3 days from the last dose of the concomitant strong CYP3A inhibitors and/or P-gp inhibitors.

Table 5.1 Dose Delays and Modifications for Concomitant Strong CYP3A Inhibitors and/or P-gp Inhibitors

Inhibitor	DS-3201b Dose	
	200 mg Once Daily	150 or 100 mg Once Daily*
Strong CYP3A inhibitors	Reduce the dose of the study drug to 100 mg once daily	Reduce the dose off the study drug to 50mg once daily
P-gp inhibitors	Reduce the dose of the study drug to 100 mg once daily	Reduce the dose off the study drug to 50mg once daily
Drugs having a strong CYP3A inhibitory effect and a P-gp inhibitory effect	Reduce the dose off the study drug to 50mg once daily	Interrupt the study drug

CYP3A = cytochrome P4503A; P-gp = P-glycoprotein

*When the dose of study drug DS-3201b is 150mg or 100mg once daily, the investigator should consult Daiichi's medical monitor before further reduction of the dose due to concomitant use of strong CYP3A or/and P-gp inhibitors.

Table 6.0 Dose Delays and Modifications for All Other Non-Hematologic TEAEs

Toxicity Grade	Modification instructions
QTc Grade 3 (QTc >500 ms on 2 separate ECGs, or >60 ms change from baseline, as the average from triplicate), regardless of causality OR Grade 4 (Torsade de Pointes, polymorphic ventricular tachycardia, or signs/symptoms of serious arrhythmia), regardless of causality	
 For Grade 3 QTc: Interrupt administration of study drug DS-3201b immediately For Grade 3 QTc: Check and address any potentially contributing factors: 
 Check and correct electrolytes (potassium, calcium, and magnesium) For Grade 3 QTc: If possible, stop any concomitant medications that prolong QTc interval For Grade 3 QTc: Once resolved to ≤Grade 1 (QTc ≤ 480 ms, as the average from triplicate) the study drug DS-3201b may be resumed. For Grade 3 QTc: If causality is attributed to the study drug DS-3201b, reduce dose by 1 dose level in subsequent cycles For Grade 3 QTc: If the QTcF increase is assessed to be attributed to a cause other than the study drug DS-3201b, resume the study drug DS-3201b at the dose level before interruption, or at a reduced dose (by 1 dose level) but the subject must be monitored closely for QT prolongation for the first cycle at the increased dose. For Grade 3 QTc: If a second dose interruption is required due to Grade 3 QTc prolongation, discontinue subject from the study For Grade 3 QTc: For any dose delays greater than 28 days, decision regarding study continuation or discontinuation should be discussed with the study PI and Daiichi. For Grade 4 (Torsade de Pointes, polymorphic ventricular tachycardia, or signs/symptoms of serious arrhythmia), regardless of causality: Interrupt the study drug DS-3201b immediately For Grade 4 (Torsade de Pointes, polymorphic ventricular tachycardia, or signs/symptoms of serious arrhythmia), regardless of causality: Determine if there are any attributing factors such as electrolytes (potassium, calcium and magnesium), concomitant medications, or other factors For Grade 4 (Torsade de Pointes, polymorphic ventricular tachycardia, or signs/symptoms of serious arrhythmia): If causality is attributed to the study drug DS-3201b, discontinue subject from study For Grade 4 (Torsade de Pointes, polymorphic ventricular tachycardia, or signs/symptoms of serious arrhythmia): If causality is not attributed to the study drug DS-3201b, study drug administration of DS-3201b can resume at a reduced dose (by 1 dose level) once resolved to ≤Grade 1 (QTc ≤ 480 ms, as the average from triplicate).
Other Non-Laboratory Adverse	
 Interrupt administration of study drug DS-3201b up to 28 days.

Events (drug related Grade 3 that require treatment)	
Resume the study drug DS-3201b at the dose before interruption once resolved to \leqGrade 1 or baseline value within 28 days after interrupting study drug.If a second dose interruption is required for the same drug-related adverse event, then decrease study drug DS-3201b dose by 1 dose level for subsequent cycles. Further dose reductions must be discussed with the study PI and sponsor. If patient is already at the lowest dose of study drug, please discuss with the study PI and Daiichi regarding study continuation or discontinuation decision. Exceptions:
○ Fatigue (DS-3201b related), Grade 3, that improves within 72 hours after onset○ Nausea, vomiting, anorexia, or diarrhea (DS-3201b related), Grade 3, that improves to \leqGrade 2 within 72 hours after onset with appropriate supportive therapy
Other Non-Laboratory Adverse Events (Grade 4, regardless of causality)	
Interrupt administration of study drug DS-3201b up to 28 days.If causality is attributed to study drug DS-3201b, resume the study drug DS-3201b at a reduced dose (by 1 dose level) for the subsequent cycles once resolved to \leqGrade 1 or baseline condition.If causality is not attributed to the study drug DS-3201b, resume the study drug DS-3201b at the dose before interruption or at a reduced dose (by 1 dose level).If second dose interruption is required due to the same drug-related adverse event, discontinue subject from the study.For any dose delays greater than 28 days, decision regarding study continuation or discontinuation should be discussed with the study PI and sponsor.
Other Laboratory Adverse Events (DS-3201b drug related Grade 3 that require treatment)	
Interrupt administration of study drug DS-3201b up to 28 days.Resume the study drug DS-3201b at the dose before interruption once resolved to \leqGrade 1 or baseline value within 28 days after interrupting study drug.If a second dose interruption is required for the same drug-related adverse event, then decrease study drug DS-3201b dose by 1 dose level for subsequent cycles. Further dose reductions must be discussed with the study PI and sponsor. If patient is already at the lowest dose of study drug, please discuss with the study PI and Daiichi regarding study continuation or discontinuation decision. Exceptions:
○ Transient laboratory abnormalities (DS-3201b-related) that do not involve associated clinical signs or symptoms and that resolve within 72 hours after onset

	
For any dose delays greater than 28 days, decision regarding study continuation or discontinuation should be discussed with the study PI and sponsor.
Other Laboratory Adverse Events (DS-3201b drug related Grade 4)	
Interrupt administration of study drug DS-3201b up to 28 days.Resume the study drug DS-3201b at a reduced dose (by 1 dose level) for the subsequent cycles once resolved to \leqGrade 1 or baseline conditionIf a second dose interruption is required for the same drug-related adverse event, discontinue subject from studySubjects who experience a \geqGrade 3 laboratory AE who are, in the opinion of the investigator, benefiting from treatment may be allowed to continue study drug.
Other Non-Laboratory and Laboratory Adverse Events (regardless of causality, any AE, lab abnormality or intercurrent illness that presents a substantial clinical risk to the subject with continued dosing per the investigator's opinion)	
Interrupt administration of study drug DS-3201b until there is no longer a substantial clinical risk to the subject with continued dosing of the study drug DS-3201b per the investigator's opinionResume the study drug DS-3201b at the same dose level
AEs Grade 1-2	
Proceed with full-dose treatment of all agents.

If DS-3201b needs to be held for any TEAEs as above, irinotecan should be held as well. When both study drugs are held for any particular visit due to TEAEs, counting of dose cycles will hold until their TEAEs have resolved or improved enough to meet protocol guidelines to restart treatment with both study drugs. If both drugs are held longer than 1 cycle (21 days), the treating physician must discuss eligibility for the patient to continue treatment on study with the study PI.

